8.1. Sample size

Randomisation into expansion, extraction and control will be applied for patients without cross-bite having lack of space and – based on canine position and angulation - belonging to strata nCLB and nCLA. Within each of both strata, a randomisation will be performed using permuted blocks of varying size, yielding an equal number of patients in each of the three groups.

Success of the approach is defined as eruption without necessity of surgical intervention and integrity of the roots of the adjacent teeth. The primary endpoint is defined as the percentage success after 18 months. The trial is powered to show a difference between any of the pairs of groups. To have at least 80% power to show a higher success rate in one group compared to the other group, there are 78 subjects needed in each group assuming a success rate of 50% in the first group and 75% in the second group. The calculation is based on a two-sided χ^2 -test with alpha set at $0.05/3=0.0167$ to control the family-wise error rate at 5% (3 pairwise comparisons). However, to increase the amount of information for the development of a prediction model for success at 18 months (cfr. second aim of the study) it has been decided to increase the number of patients to 100 per group (300 patients in total).

8.2. Analysis

The analysis of the primary endpoint will be based on a stratified χ^2 -test using a Bonferroni-Holm correction to correct for multiple testing (the strata are nCLB and nCLA). The same approach will be used for the comparison at the earlier timepoints (6 and 12 months). No interim analyses are planned, neither for efficacy, nor for futility. The analysis will be performed on an intent-to-treat basis.

A multivariable logistic regression model will be used to predict maxillary permanent canine impaction (=lack of success) on all included subjects. A backward selection procedure will be applied with 0.157 as critical level for the p-value. This critical value corresponds to the use of the Aikake Information Criterion (AIC) for model selection. With AIC we require that the increase in model χ^2 has to be larger than two times the degrees of freedom. This strategy provides a trade-off between erroneous inclusion and exclusion of covariates in a prediction model (Sauerbrei W. The use of resampling methods to simplify regression models in medical statistics. *Applied Statistics* 1999;48 (3):313–329.). The considered predictors are: strata formed by presence of cross-bite and parameters related to canine position and angulation, non-eruption, interceptive strategy, patient's age, stage of canine root formation, premature loss of deciduous teeth, familial history, space deficiency (arch length discrepancy).

As a sensitivity analysis, the prediction model will also be applied separately on the patients from the randomized and non-randomized part of the study.

9. Quality assurance

During this randomized clinical trial only standard operating procedures will be employed, such as i.e. removable expansion device, fixed expansion device, headgear, etc.. They are all validated, thoroughly described and widely used techniques. It will be up to the treating professional to decide for a given case which procedure to follow, in line with existing traditions in the specific collaborating centres. However, the main purpose should be attained which is expansion or in other words gaining extra space for tooth alignment. Depending on the interceptive treatment to be accomplished, decision will be taken to employ one specific treatment protocol to reach the goal set forward.

Randomisation will only be used when the different treatment options could be equally beneficial to the patient, with the objective of identifying possible differences in treatment outcomes. There is no new intervention to test, which minimizes the risk for negative impact.

10. Direct access to source data and documents

The investigators and the involved institutions will permit trial-related monitoring, audits, EC review, and regulatory inspections (where appropriate) by providing direct access to source data and other documents (i.e. patients' case sheets, X-ray reports, etc.).

11. Ethics and regulatory approvals

The trial will be conducted in compliance with the principles of the Declaration of Helsinki (2013), the principles of GCP and in accordance with all applicable regulatory requirements. This protocol and related documents will be submitted for review to the Ethics Committee of the UZ/KU Leuven for Clinical Trial Authorization.

The Study can and will be conducted only on the basis of prior informed consent by the Subjects, or their legal representatives, to participate in the Study. The Participating Site shall obtain a signed informed consent form (ICF) for all patients prior to their enrolment and participation in the Study in compliance with all applicable laws, regulations and the approval of the UZ/KU Leuven Ethics Committee. The Participating Site shall retain such ICFs in accordance with the requirements of all applicable regulatory agencies and laws.

The Investigator and the Participating Site shall treat all information and data relating to the Study disclosed to Participating Site and/or Investigator in this Study as confidential and shall not disclose

such information to any third parties or use such information for any purpose other than the performance of the Study. The collection, processing and disclosure of personal data, such as patient health and medical information is subject to compliance with applicable personal data protection and the processing of personal data (Directive 95/46/EC and Belgian law of December 8, 1992 on the Protection of the Privacy in relation to the Processing of Personal Data).

In this study, data will be coded.

*(Data are **anonymous** if no one, not even the researcher, can connect the data to the individual who provided it. No identifying information is collected from the individual.*

*When data are **coded**, there continues to be a link between the data and the individual who provided it. The research team is obligated to protect the data from disclosure outside the research according to the terms of the research protocol and the informed consent document. The subject's name or other identifiers will be stored separately from their research data and replaced with a unique code to create a new identity for the subject, as coded data are not anonymous.)*

12. Data Handling

The patient's data (radiographs, follow up reports, ...) will be stored in the patient's electronic folder, without linking it to the study. A randomization list will be electronically made in order to manage the allocation of the patients. Everything related to the University Hospitals Leuven patient treatment will be stored on the University Hospitals Leuven database. In case of further use of the data (for statistical purpose, etc.), the identity of the patients will remain anonymous.

13. Data Management

All data will be managed electronically, except for the informed consent (included in our regular contract for orthodontic treatment), a copy of which will be printed in paper for the patient and parents. A signed copy will be electronically saved with the rest of the data in the University Hospitals Leuven database.

14. Translational research

No biological material will be collected/shipped/stored/used for the study.

15. Publication Policy

As it is an international multicentre trial:

It is anticipated that the results of the overall Study will be published in a multi-centre publication, involving the data of all clinical sites participating in the Study.

The Participating Site is not allowed to publish any data or results from the Study prior to the multicentre publication, provided however that Participating Site is allowed to publish the results generated at the Participating Site if the multicentre publication has not occurred after 12 months from Study database lock.

Any publication by Participating Site will be submitted to the Sponsor for review at least thirty (30) days prior to submission or disclosure. Sponsor shall have the right to delay the projected publication for a period of up to three (3) months from the date of first submission to the Sponsor in order to enable the Sponsor to take steps to protect its intellectual property rights and know-how.

Publications will be coordinated by the Investigator of Sponsor. Authorship to publications will be determined in accordance with the requirements published by the International Committee of Medical Journal Editors and in accordance with the requirements of the respective medical journal.

16. Insurance/Indemnity

In accordance with the Belgian Law relating to experiments on human persons dated May 7, 2004, University Hospitals Leuven shall assume, even without fault, the responsibility of any damages incurred by a Study Patient in the Leuven Centre and linked directly or indirectly to the participation to the Study, and shall provide compensation therefore through its insurance.

If an insurance coverage is required by local laws of Participating Site, the Participating Site shall have and maintain in full force and effect during the term of this Agreement (and following termination of the Study to cover any claims arising from the Study) adequate insurance coverage for possible damages linked directly or indirectly to the patients' participation to the Study at Participating Site.

17. Financial Aspects

There are no financial issues, meaning that this randomized clinical trial is not financially supported by any third party. Every Participating Site will manage its randomized clinical trial autonomously.

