6.	Assessment of efficacy	15
7.	Assessment of safety	16
7.1.	Specification, timing and recording of safety parameters	16
7.2.	Procedures for recording and reporting adverse events (AE).....	16
7.3.	Treatment stopping rules.....	16
8.	Statistics	16
8.1.	Sample size	17
8.2.	Analysis.....	17
9.	Quality assurance	18
10.	Direct access to source data and documents.....	18
11.	Ethics and regulatory approvals.....	18
12.	Data Handling.....	19

13. Data Management.....	19
14. Translational research	19
15. Publication Policy	19
16. Insurance/Indemnity	20
17. Financial Aspects	20

1. Study Synopsis

Title of clinical trial	Effect of interceptive strategies on the clinical outcome of impacted maxillary permanent canines.
Protocol Short Title/Acronym	Impacted Canines
Sponsor name	UZ Leuven
Principal Investigator	[name]. [name]
Medical condition or disease under investigation	Maxillary permanent canine impaction
Purpose of the clinical trial	Prospective interventional study of maxillary permanent canines using classic interceptive measures for preventing impaction
Primary objective	To define the most optimal interceptive action for prevention of maxillary permanent canine impaction
Secondary objective (s)	To predict the risk of maxillary permanent canine impaction in young children
Trial Design	International Prospective Interventional Study
Endpoints	Eruption of maxillary permanent canines into the occlusal plane of the dentition.
Sample Size Estimation	For 80% power, 78 subjects needed in each group (for a 50% (nCLA) and 75% success rate (nCLB)). To increase the amount of information for the development of a prediction model for success at 18 months (2nd aim of the study) we need to increase the sample to 100/group (300 patients in total).
Summary of eligibility criteria	Untreated impacted maxillary canines with incomplete root formation, no resorption, no syndromes, no radiotherapy
Maximum duration of interceptive treatment of a subject	6 months
Minimum duration of interceptive treatment follow-up of a subject	6-18 months
Version and date of final protocol	Version 4.0 April 18, 2016
Version and date of protocol amendments	

2. Background and rationale

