3.1. Trial objectives and definitions

The purpose of this study is to detect the differences, if any, between three well known, validated interceptive measures in case of maxillary permanent canine impaction, and to prospectively follow up on these treated patients until further permanent canine alignment in the dental arch is achieved. This long term follow up is necessary in order to evaluate the effects of the interceptive treatment on permanent maxillary canine eruption.

In the present study, a **maxillary permanent canine impaction** would be defined as the inability of this tooth to erupt, failure of eruption, deviation of the canine from its normal eruption pathway or retention of the canine in the maxilla.

Success of a particular interceptive measure would be defined as eruption of the canine without the need for surgical intervention and integrity of the adjacent teeth.

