3.2. Primary endpoints

The primary objective is to search for the most optimal interceptive action to prevent maxillary permanent canine impaction.

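### Optional: Bonferroni-Holm in 8.2 is valid, but with exactly three arms its second step is stricter than needed, and Shaffer's step-down gains up to about 8 points of power for no extra patients

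*Combined protocol and SAP*

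**What the plan says.** Section 8.1 randomises patients in strata nCLA and nCLB equally to expansion, extraction or control. It states the power goal as "The trial is powered to show a difference between any of the pairs of groups". The sizing is 78 per arm for at least 80% power, "assuming a success rate of 50% in the first group and 75% in the second group", using a two-sided chi-square test at 0.05/3 "to control the family-wise error rate at 5% (3 pairwise comparisons"). The number is then raised to 100 per arm to support the prediction model.

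Section 8.2 analyses success at 18 months with a stratified chi-square test "using a Bonferroni-Holm correction to correct for multiple testing (the strata are nCLB and nCLA"). It adds: "The same approach will be used for the comparison at the earlier timepoints (6 and 12 months").

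On aims, 3.1 says "The purpose of this study is to detect the differences, if any, between three well known, validated interceptive measures", and 3.2 says "The primary objective is to search for the most optimal interceptive action to prevent maxillary permanent canine impaction". Neither section gives a decision rule for naming one arm the best. The documents mention neither closed testing nor the logical link between the three pairwise hypotheses.

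**The concern.** Holm's thresholds of 0.05/3, 0.05/2 and 0.05 suit any three hypotheses, related or not. The three pairwise equalities among three arms are related: if A differs from B, then A = C and B = C cannot both hold. Holm's second threshold guards against two true nulls remaining after a correct rejection, which cannot happen here.

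What is at stake is the second and third comparisons. Ranking three measures normally takes more than one rejection, so the aims in 3.1 and 3.2 depend on the threshold used after the first. A rule with the same nominal family-wise control, first step, test and sample size, which rejects everything Holm rejects, is worth having if it costs a sentence.

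**Working it through.** **Inputs.** From 8.1: three arms, three pairs, equal allocation, 50% vs 75%, two-sided 0.05/3, 78 and 100 per arm. From 8.2: stratified chi-square test with Holm. Assumed, because the documents do not say: equal stratum sizes, no dropout, no continuity correction, and a range of third-arm rates.

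**Step 1: the plan's own figure.** With pooled variance and no continuity correction,

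n = [z(1 − α/2)·√(2·p̄·(1 − p̄)) + z(0.80)·√(p1(1 − p1) + p2(1 − p2))]² / (p2 − p1)²

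Put in p1 = 0.50, p2 = 0.75, p̄ = 0.625, α = 0.05/3, z = 2.394 and 0.842:

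[2.394 × 0.6847 + 0.842 × 0.6614]² / 0.0625 = 77.1, so 78 per arm.

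The stated 78 is reproduced. With a continuity correction the answer would be 85, so the sizing matches the uncorrected test.

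**Step 2: thresholds.**

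| Step | Holm | Shaffer, three arms |
|---|---|---|
| Smallest p | 0.05/3 | 0.05/3 |
| Second p | 0.025 | 0.05 |
| Largest p | 0.05 | 0.05 |

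The argument carries over to the stratified test, since each pairwise null is equality within both strata.

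**Step 3: power of one 50% vs 75% test at each level (formula).**

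| Per arm | 0.0167 | 0.025 | 0.05 |
|---|---|---|---|
| 78 | 80.5% | 84.6% | 90.5% |
| 100 | 90.4% | 92.8% | 96.0% |

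**Step 4: simulation of the whole procedure.** At least 300,000 trials per scenario, 100 per arm, two equal strata, pairwise stratified tests. Two arms are at 50% and 75%; the third varies. The table gives the chance that the 75% arm beats both others.

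| Third arm | Holm | Shaffer | Gain (points) |
|---|---|---|---|
| 30% | 95.8% | 96.0% | about 0.1 |
| 40% | 94.2% | 95.9% | about 1.6 |
| 50% | 87.6% | 92.0% | 4.4 |
| 55% | 74.7% | 81.6% | 6.9 |
| 60% | 52.3% | 60.5% | about 8 |
| 62.5% | 39.3% | 47.0% | 7.7 |
| 70% | 9.9% | 12.2% | 2.3 |
| 73% | 4.9% | 5.8% | 0.9 |

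At a third-arm rate of 25% there is no gain. The chance of at least one rejection is the same under both rules: 97.1% at 50/50/75% and 91.4% at 50/62.5/75%. Shaffer rejected everything that Holm rejected.

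Power for the 50% vs 75% pair itself moves little: 92.4% to 94.6% with the third arm at 50%, and 90.8% to 91.2% with it at 62.5%.

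**Step 5: error on a truly equal pair (same simulation).**

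| Rates | Holm | Shaffer |
|---|---|---|
| 50/50/75% | about 4.8% | about 5.6% |
| 50/75/75% | 4.2% | about 4.9% |
| 50/50/80% | about 5.4% | about 5.6% |
| 50/50/85% | about 5.6% | about 5.6% |

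With all arms at 50%, the error is the same under both, about 4.8%. The 5.6% is the actual size of one uncorrected chi-square test at nominal 0.05 with these numbers. Holm reaches it once the third arm is so far away that the other two pairs are nearly always rejected.

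**The case against.** The strongest objection is that there is no defect. Holm is valid, 8.1 asks for 80% power on a pair, and 100 per arm already gives 90.4% at the strictest level. For that contrast the gain is only 0.4 to 2.2 points at the third-arm rates examined (50% and 62.5%). This stands, and it is why the point is optional. It does not make the choice mere taste, because the alternative rejects at least as much at the same nominal family-wise level.

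Second, the larger gains use a criterion that the plan does not set. That the best arm should beat both others is our reading of the aim in 3.2. The third-arm rate is also ours, and a control arm well below both active arms is possible, in which case the gain vanishes. This stands too, so the range has to start at about zero.

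Third, 8.2 does not say whether the test is continuity-corrected. That it is not is inferred from the 78 in 8.1, which concerns sizing rather than analysis. It remains an assumption.

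Three stronger readings are tempting and not supported:

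- *Section 8.2 is wrong or the trial is underpowered.* The stated sizing reproduces, and Holm can only add to it.
- *Keeping Holm holds the error at 5%.* The excess comes from the uncorrected test, and Holm has the same worst case.
- *The Synopsis shows that the strata are being compared.* It reads "For 80% power, 78 subjects needed in each group (for a 50% (nCLA) and 75% success rate (nCLB")), but 8.1 and 8.2 use nCLA and nCLB as strata. This is a wording slip that changes no number and carries no weight here.

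**Conclusion.** An optional, cheap improvement. The multiplicity method in 8.2 is valid but more conservative at its second step than three arms require. Under the stated assumptions the chance of separating the best arm from both others rises by about 0 to 8 points: largest when the third arm lies around 60%, near zero when it is at 30% or lower, and about 1 point when it nearly ties with the best. The cost in error is less than one percentage point on a truly equal pair in the scenarios examined, with the same ceiling that Holm already has. No gain is claimed at 6 and 12 months, for which the documents give no success rates. Confidence in the logic is high; the size depends on a third-arm rate that nobody has stated.

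**What to change.** Before outcome data are seen, replace the Bonferroni-Holm wording in 8.2 with: *compare the smallest of the three pairwise p-values with 0.05/3; if it is significant, test each of the other two at 0.05 (Shaffer's step-down).* Use the same rule at 6 and 12 months for consistency, and say in the same place whether the stratified test is continuity-corrected.

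The rule costs one sentence, with no added patients or data. The first step is unchanged, so the 78 and 100 per arm stand. The price is part of Holm's slack, as shown in step 5. A sponsor who wants no excess over 5% must look to the test, not to the step-down; a continuity-corrected test would make the sizing 85 per arm and is not proposed here.

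As a separate editorial matter, reword the Synopsis sample-size entry so that the 50% and 75% belong to two treatment arms, as in 8.1.

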3.3. Secondary endpoints

The secondary objective is to evaluate whether based on the observations of the present study prediction of maxillary permanent canine impaction in young children is feasible.

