Patients in **Subgroup nCLA**, constituting patients with no cross bite present but lacking space for adequate tooth alignment in the dental arch, will be randomly attributed to one of our three usual treatment options, being interceptive maxillary expansion (IME), extraction of the deciduous canines (EXIII), or no treatment (CO). The latter will constitute the control group within Group nCLA, indicative for maxillary permanent canine eruption in case of lack of space in the dental arch. After this interceptive treatment, all the patients will be enrolled in a standard follow up protocol. In case of absence of deciduous maxillary canines, randomization will not be possible. These patients will still be treated with expansion because of the lack of space and will also be enrolled in subsequent follow-up.

Patients in **Subgroup nCLB** will also be randomly attributed to one of these three usual treatment protocols, being interceptive maxillary expansion (IME), extraction of the deciduous canines (EXIII), or no treatment (CO). The latter will constitute the control group within Subgroup nCLB. After this interceptive treatment, all the patients will be enrolled in a standard follow up protocol. In case of absence of deciduous maxillary canines, randomization will not be possible. These patients will still be treated with expansion because of the lack of space and will also be enrolled in subsequent follow-up.

Subgroup nCLC, constituting the patients with no cross bite present but lacking space for adequate tooth alignment in the dental arch and with very badly positioned and angulated permanent maxillary canine(s), will receive interceptive maxillary expansion (IME) using the standard expansion techniques described above and commonly applied in the university hospital. Patients in Subgroup nCLC, after receiving interceptive expansion treatment, will be further subjected to extraction of the deciduous canine at 6month follow-up, whenever still present in the dental arch, as well as, depending on the severity of canine angulation and position, of the first deciduous molar. Decision for extraction of one or both of these deciduous teeth will be the responsibility of the treating dentist who will have to evaluate the clinical circumstances presenting in this patient with

very badly positioned permanent maxillary canines. Sequence of eruption other than 3-4-5 will also constitute a criterion for extraction of these deciduous teeth.

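### Backward selection may remove interceptive strategy from the prediction model, although strategy is set by design and randomised in nCLA and nCLB

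*Combined protocol and SAP*

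**What the plan says.** Section 8.2 (Analysis) specifies the model: "A multivariable logistic regression model will be used to predict maxillary permanent canine impaction (=lack of success) on all included subjects". The selection rule follows: "A backward selection procedure will be applied with 0.157 as critical level for the p-value". The text equates this level with AIC and defends it as a balance between wrongly including and wrongly excluding covariates.

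The candidate list contains, among others, "non-eruption, interceptive strategy, patient's age, stage of canine root formation". No predictor is exempt from elimination. The only sensitivity analysis applies the model separately to the randomised and non-randomised patients, without protecting the treatment term.

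The aim is worded in the synopsis as "To predict the risk of maxillary permanent canine impaction in young children", and section 3.3 asks whether "prediction of maxillary permanent canine impaction in young children is feasible". Neither place says under which treatment the risk is meant.

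Section 8.1 randomises nCLA and nCLB patients to expansion, extraction or control, "yielding an equal number of patients in each of the three groups". It raises the size from 78 to 100 per group specifically to support the prediction model.

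**The concern.** In nCLA and nCLB, strategy is assigned by the trial itself and its contrast is identified by randomisation. Whether it stays in the model should not depend on a p-value. If it is eliminated, the fitted risk in these strata refers to a mixture of one third untreated and two thirds treated patients. That mixture is an artefact of the allocation ratio and matches no child seen in practice. Because the plan does not state the treatment condition of the predicted risk, a user could not tell from the final model which risk is being read. The extra 22 patients per group were added for this model, so its output should have a defined meaning.

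**Working it through.** **Inputs from the documents.** Three equal arms, 100 per arm; planned success 50% v 75%; two-sided alpha 0.05/3; elimination level 0.157. **Assumed:** success rates of 65%, 60% and 55% in the treated arms, and equal rates in the two treated arms.

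**1. The plan's own sample size.** Pooled-variance formula for two proportions, with mean 0.625, z(1 − 0.0167/2) = 2.394 and z(0.80) = 0.842:

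n = [2.394·√(2·0.625·0.375) + 0.842·√(0.5·0.5 + 0.75·0.25)]² / 0.25² = 77.1, rounded up to 78.

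The stated 78 is reproduced. Power is 80.5% at 78 and 90.3% at 100 per group.

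**2. Critical value.** Three strategies use 2 degrees of freedom. A p-value of 0.157 on 2 df corresponds to a chi-square of 3.70. (0.157 equals AIC for 1 df only. The rule of twice the degrees of freedom gives chi-square 4, p = 0.135, on 2 df, which makes removal slightly more likely.)

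**3. Chance of removal.** Noncentral chi-square on 2 df, with noncentrality λ = 100·Σ(pᵢ − p̄)² / [p̄(1 − p̄)].

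| Success: control / treated / treated | p̄ | λ | P(removed) |
|---|---|---|---|
| 50/75/75 | 0.667 | 100·0.04167/0.2222 = 18.75 | 0.5% |
| 50/65/65 | 0.600 | 100·0.0150/0.2400 = 6.25 | 21% |
| 50/60/60 | 0.567 | 100·0.00667/0.2456 = 2.71 | 49% |
| 50/55/55 | 0.533 | 100·0.00167/0.2489 = 0.67 | 75% |

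A simulation of the likelihood-ratio test (400,000 runs per scenario) gives 0.5%, 21.3%, 49.3% and 74.5%. With no effect at all, removal occurs in 84%. Under the chi-square > 4 rule, the 50/60/60 figure becomes 52.0%.

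**4. Size of the error.** After removal, the model shows the pooled failure rate. Removal is more likely when the control arm happens to do well, so the control arm's own observed failure is also below 50% in those datasets. A model that keeps strategy is unbiased overall here. The average error of selection is therefore P(removed) × (pooled failure − observed control failure), both given removal.

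| Scenario | Pooled failure given removal | Observed control failure given removal | Average error over all datasets |
|---|---|---|---|
| 50/65/65 | 40.0% | 44.8% | 0.21 × (−4.8) = −1.0 points |
| 50/60/60 | 43.3% | 47.0% | 0.49 × (−3.7) = −1.8 points |
| 50/55/55 | 46.7% | 48.7% | 0.75 × (−2.1) = −1.5 points (difference from unrounded values) |

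At 50/75/75 the average error is below 0.1 point, because removal is so rare.

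**5. Root mean squared error of the untreated failure risk, selection v strategy kept.** 6.3 v 5.0 points at 65/65, 6.3 v 5.0 at 60/60, 5.0 v 5.0 at 55/55, and 4.0 v 5.0 with no effect.

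**6. Check with strata in the model.** The documents give no sizes for the non-randomised groups. An assumed cohort of 300 randomised, 60 cross-bite and 100 untreated nCN patients, with a log odds ratio of 0.4, gave about 50% removal. Given removal, untreated risk was understated by about 6 points in the randomised strata. This agrees with the simpler calculation.

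**The case against.** The best defence is that section 8.2 chose its threshold knowingly and gives a reason for it. Removal is almost excluded at the effect the trial is powered for. Where it is likely, the effect is small and the average error is only 1 to 2 points. In the datasets where removal happens, a model that keeps strategy is itself off by 5.3, 3.0 and 1.3 points, so removal adds about 4.8, 3.7 and 2.1. If strategy has no effect, selection is the more precise choice. Outcomes by arm will also be available from the primary analysis.

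Most of this stands and limits the size of the point. It does not answer the question of meaning. The stated trade-off concerns covariates in general, not a factor the trial assigns. The separate fit on randomised patients can lose the same term, and the primary comparison gives arm-level rates, not individual risks.

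Three stronger readings are tempting, but the documents do not support them.

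- **The prediction would rest on mostly treated patients.** This is shown only for the randomised part (200 of 300). Section 3.4 leaves nCNA and nCNB untreated and their sizes are not given. With t treated and u untreated non-randomised patients, the treated share (200 + t)/(300 + t + u) is 50% or less once u reaches 100 + t.
- **The plan misses its target of untreated risk.** No such target is stated. The defect is an unspecified treatment condition.
- **Later extractions create a spurious harmful effect.** Section 3.4 says that nCLC patients "will be further subjected to extraction of the deciduous canine at 6month follow-up, whenever still present in the dental arch", and extraction in CC also follows expansion. If strategy were coded as received, later events could enter a baseline model. However, the plan does not say that it is coded so, gives no success rates from which to size such an effect, and does not randomise these groups.

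**Conclusion.** The concern holds in limited form. Section 8.2 allows a factor set by design to be removed by a p-value. If that happens, predicted risk in nCLA and nCLB is an average over the allocation ratio. Removal is realistic for modest effects (about 21% to 75% of datasets for treated-arm success of 65% down to 55%) and very unlikely at the planned 75%. Given removal, untreated failure is understated by about 10, 7 and 3 points; over all datasets the understatement is about 1 to 2 points.

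These figures rest on assumed treated-arm rates (other than 75%), equal effects in the two treated arms, and the randomised patients analysed without other covariates. The point concerns a secondary analysis. It is a cheap improvement and does not threaten the trial's main conclusion.

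**What to change.** In section 8.2:

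1. Keep interceptive strategy in the model whatever its p-value, and apply backward elimination only to the other predictors. Do the same in the separate fits wherever strategy varies.
2. Code strategy as the randomised arm for randomised nCLA and nCLB patients, and state the coding for everyone else. That includes children without deciduous canines in those subgroups, and cyst cases, who belong to no group.
3. Report predicted risk by stated strategy. Give a no-treatment risk only for groups with untreated patients: nCLA, nCLB, nCNA and nCNB. For groups C, nCLC and nCNC no untreated patients are planned, so such a figure would be extrapolation.

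The cost is a few sentences. Two degrees of freedom are always spent on strategy, or three if expansion followed by extraction is its own category. That category would occur only in CC and nCLC and so be nearly determined by stratum. If strategy has no effect, precision is slightly lower (root mean squared error 5.0 v 4.0 points). Design, data collection and the primary analysis do not change.
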